4.5 Study Procedures/Intervention

4.5.1 Psoas Compartment Block Administration

Following exposure, the rectus femoris muscles are elevated with a two-prong retractor, thus exposing the iliopsoas muscle. An 18G spinal needle is inserted to a depth of 0.5-1.0 cm under the fascia at the level of the musculotendinous junction or more proximally, and 0.3% ropivacaine in 50 mL are administered into the psoas compartment. The local anesthetic travels proximally and anesthetizes a portion of the lumbar plexus specifically targeting the obturator, femoral, and lateral femoral cutaneous nerves to provide local pain control.

4.5.2 Local Anesthetic Infiltration Administration

A combination of medications including 30 mL 0.5% ropivacaine, 0.15 mg epinephrine, 4 mg morphine, and 30 mg toradol (hereby referred to as "cocktail") will be diluted with 19 mL of 0.9% NaCl and will be injected into the tissues surrounding the hip joint in a systematic fashion ensuring uniform delivery to all tissues incised and instrumented. This cocktail is infiltrated into the periarticular tissues including muscle, joint capsule, and subcutaneous tissues at the surgeon's discretion. We will use the following technique, which will be standardized amongst all patients: joint capsule, rectus femoris direct and reflected head, tensor fascia lata, and subcutaneous tissues circumferentially every 25 mm.

4.5.3 Postoperative Pain Management Protocol

All patients will follow [name] standard of care pain management protocol. There may be slight differences in the amount of pain medication given to the patients' intra- and postoperatively at the anesthesiologist's and/or nurse anesthetist's discretion.

4.6 Data Collection

- Primary outcome variable: VAS Pain scores measured at times in Appendix I: Table I
- Secondary outcome variable: Total amount of opioid usage in-hospital (and with 24 hours and 24-48 hours postoperatively)

Demographic and Operative Variables

- Sex
- Age
- Race
- BMI
- ASA score
- Comorbidities, as recorded by anesthesiology
- Date of Surgery
- Time of Surgery
- Laterality (left/right)
- Operative Time (skin incision to skin close, mins)
- Estimated Blood Loss (mL)
- Intraoperative Complications (fracture, bleeding events, etc.)

Outcomes Variables

- Narcotic Use (expressed in oral morphine equivalent units)
- Non-narcotic pain medication usage
- Major Postoperative Complications (DVT, Falls, Infection, etc.) through first postoperative visit
- Units of blood transfused
- Complications related to block/anesthetic
- VAS Resting Pain Scores
- VAS Ambulating Pain Scores
- Time of First Physical Therapy Session
- Length of Hospital Stay (Days)
- Readiness for discharge (days), requiring the following:
 - A pain score of <4 (numeric rating scale) without non-oral narcotics

- Normal eating
- Minimal nausea
- Urination without a catheter
- A dry surgical wound
- No acute medical problems
- The ability to independently transfer and walk 100 feet
- Stable vitals

Pain will be measured on a numeric Likert scale, rating the pain from 0 (none) to 10 (maximal). Scores will be collected at 3 hours postoperatively, in the morning and afternoon on postoperative day one and two and at the post-operative clinic visit. The patient will record their pain on a data collection form that is given to them at each time point. Pain will be recorded for when the patient is at rest and when the patient is ambulating. On postoperative day one and postoperative day two the patient will be asked to fill out the Quality of Recovery Score [Myles] and Opioid-Related Symptom Distress Scale [Apfelbaum, Yadeau] (Appendix I: Table I).

All pain medications will be prescribed per standard of care. Pain medication usage in-hospital will be recorded from Epic. All opioid consumption will be converted to oral morphine equivalents in milligrams. All demographic and operative variables will also be collected for each patient from electronic medical records.

Readiness for discharge will be assessed in both the morning and evening of each postoperative day.

4.7 Statistical Analyses

A table of descriptive summaries on demographic and operative variables by treatment group will be prepared (means and standard deviations if normally distributed, median and range if not normally distributed, counts and percentages for categorical variables); inference procedures which are consistent with the chosen variable summaries will be used to compare treatment groups.

Before analyzing continuous variables, data sets will be assessed for normality using a Shapiro-Wilk Test and equal variance using the Levene-test. For normal data an independent Student's t-test will be used to compare means, and a Mann-Whitney Rank Sum Test will be used for data that is not normally distributed. The two treatment groups will be compared on categorical variables using the Chi-Square test or a Fisher Exact test for low frequency occurrences.

VAS Pain scores (resting, ambulating) will be compared between groups at each time point using a Mann-Whitney Rank Sum test. A Bonferroni correction will be used to

account for repeated measures and control for a Type I error. A p -value below $.05/6 = .0083$ at each individual postoperative time point will be considered statistically significant. Opioid usage will be compared for total in-hospital as well as broken down by use a 24 hours and use from 24-48 hours using the Mann-Whitney Rank Sum test. A p -value below $.05/3 = .017$ at each individual postoperative time point will be considered statistically significant. Composite scores and subscores of the Quality of Recovery-40 and Opioid-related Symptom Distress Scale, as well as the time to readiness for discharge, will be compared between groups with the t -test or Mann-Whitney Rank Sum test as appropriate.

For all other tests which do not include Bonferroni adjustment, a two-sided p -value < 0.05 will be considered statistically significant. Missing data will be treated as such; there will be no imputation. An exploratory subgroup analysis will also be performed, excluding patients with longer than 3 day stay or patients that required additional surgical intervention. Confidence intervals for the difference in means/medians/odds ratios between the two groups will also be calculated where appropriate. Graduate-trained engineers will analyze data with SPSS statistical software (SPSS Version 20.0, IBM, Inc).

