2.0 OBJECTIVE

- The primary objective of this study is to examine whether there is a difference in the level of resting pain following total hip arthroplasty with use of a psoas compartment block versus a periarticular local anesthetic infiltration.
- The secondary objective is to examine whether there is a difference in the amount of in-hospital opioid drug use postoperatively

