4.4 Randomization

The 100 patients in the study will be randomized in a 1:1 ratio to have their procedure performed either with a psoas compartment block or with local anesthetic infiltrate. Randomization assignments will be contained in sequentially numbered, opaque, sealed envelopes, which will be prepared by a statistician in the Research Institute using blocked randomization from The SAS System for Windows version 9.3. After the patient is consented, the consentor will assign the patient to a group following the treatment listed in the envelope and inform the surgeon. Logs will be maintained by consenting personnel to ensure the list is being followed and each patient's group is documented.

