8.0 APPENDIX I

Table I. Schedule of Events

Study Procedures	Screening	Surgery	3 hours postop	POD1 9 AM	POD1 5 PM	POD2 9 AM	POD2 5 PM	3 weeks postop
Visit Windows	-21 to 0 days	N/A	± 1 hours	± 2 hours	± 3 hours	± 2 hours	± 3 hours	± 1 week
Review inclusion and exclusion criteria	X							
Informed consent review and signature	X*							
Study Group Determination (Randomization)	X*							
Intervention (psoas block or periarticular injection)		X						
Collect resting pain score	X ^a		X	X	X	X ^b	X ^b	X
Collect pain with ambulation	X ^a			X ^c	X ^c	X ^{b,c}	X ^{b,c}	X ^c
Quality of Recovery-40 assessment				X		X ^b		
Opioid-related symptom distress scale assessment				X		X ^b		
Assess for adverse events			X	X	X	X	X	X

POD = postoperative day

*Consent will happen before any study procedures or assessment are done and randomization will occur at that time

a. Collected as standard of care in the clinic

b. If patient has been discharged before this time point assessments will not be collected

c. If patient is not ambulating they will have the option of selecting 'N/A'

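### Resting pain is tested without adjustment although a screening score is scheduled; one prespecified baseline-adjusted rank test would add precision at no data cost, by an amount that depends on an unstated correlation

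*Combined protocol and SAP*

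**What the plan says.** The primary objective (section 2.0) is to "examine whether there is a difference in the level of resting pain following total hip arthroplasty" between the two techniques, and section 3.0 refers to six postoperative times. Under section 4.7, resting and ambulating pain "will be compared between groups at each time point using a Mann-Whitney Rank Sum test", each at .05/6 = .0083. No covariate, change score or other use of a baseline value appears in that section.

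Table I in Appendix I marks both a resting and an ambulating score at screening, in a window of -21 to 0 days, with the footnote "Collected as standard of care in the clinic". The pain collection times listed in section 4.6 are postoperative only.

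Two other statements bear on the point. On missing data, section 4.7 says "Missing data will be treated as such; there will be no imputation". For the second postoperative day, footnote b of Table I says "If patient has been discharged before this time point assessments will not be collected".

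**The concern.** A pre-treatment measurement of the outcome is scheduled and then left out of the analysis. If screening pain predicts postoperative pain, part of the spread within each arm is explainable, and the planned test treats it as noise.

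Precision is scarce in this trial. There are 50 patients per arm, section 4.7.1 reports no sample size analysis, and the Bonferroni threshold is strict. The day-two comparisons may have fewer patients because collection stops at discharge.

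This does not make the planned test invalid. With 1:1 randomisation the unadjusted test keeps its type I error, and chance imbalance in screening pain is noise, not bias. What is at stake is power for the primary outcome. Ambulating pain is affected in the same way, at five postoperative times, because Table I has no ambulating score at 3 hours.

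**Working it through.** **Inputs from the documents.** 100 patients randomised 1:1, so 50 per arm (section 4.4); six postoperative resting scores (section 3.0, Table I); a 0-10 scale (section 4.6); threshold .0083 (section 4.7).

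**Assumed, because the documents do not say.**
- Correlation r between screening and postoperative pain: 0 to .5. It may differ between 3 hours and 3 weeks.
- True shift: 0.5 or 0.6 SD.
- Power target for the detectable difference: 80%.
- Two-sided pain tests. Section 4.7 states two-sidedness only for the tests without Bonferroni adjustment.

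**The plan's own figure.** .05/6 = .00833, and six such tests sum to .05. It reproduces. The 50 per arm cannot be checked, because no effect size, SD or power is given.

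**Detectable difference.** For the Mann-Whitney test, with large-sample efficiency 3/π relative to the t-test:

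(z(1 − .00833/2) + z(.80)) × √(2/50) / √(3/π) = (2.638 + 0.842) × 0.2 / 0.977 = 0.712 SD.

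Adjustment multiplies this by √(1 − r²):

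| r | Variance removed (r²) | Equivalent n per arm, 50/(1 − r²) | Detectable difference |
|---|---|---|---|
| 0 | 0% | 50 | 0.712 SD |
| .2 | 4% | 52.1 | 0.698 SD |
| .3 | 9% | 54.9 | 0.679 SD |
| .5 | 25% | 66.7 | 0.617 SD |

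**Simulated power.** Bivariate normal scores (assumed screening mean 5, comparator-arm postoperative mean 4.5, SD 2) were rounded and clipped to 0-10, with 20,000 trials per cell. The tie-corrected Mann-Whitney test was set against least squares of rank(postoperative score) on treatment and rank(screening score), two-sided at .05/6.

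| Setting | Mann-Whitney | Adjusted, r = 0 | r = .2 | r = .3 | r = .5 |
|---|---|---|---|---|---|
| 50 per arm, 0.6 SD | 58% | 58% | 60% | 63% | 72% |
| 50 per arm, 0.5 SD | 39-40% | 40% | 42% | 44% | 52% |
| 40 per arm left on day two (assumed), 0.6 SD | 45-46% | – | 48% | 51% | 59% |
| Floor: about 40% zeros in the comparator arm (assumed mean 1.0), 0.6 SD | 47-48% | – | 50% | 51% | 59% |

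**Missing screening scores.** With 50 per arm, a 0.6 SD shift, scores missing at random and 6,000 trials per cell:

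| Missing, r | Mann-Whitney | Adjusted, complete cases | Adjusted, missing covariate set to its mean |
|---|---|---|---|
| 5%, .2 | 58% | 57% | 60% |
| 10%, .2 | 57% | 53% | 59% |
| 10%, .3 | 59% | 58% | 63% |
| 10%, .5 | 58% | 67% | 71% |
| 20%, .3 | 59% | 51% | 63% |

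The break-even follows from the variance factor. At r = .3 adjustment leaves 91% of the variance, so losing about 9% of patients cancels it.

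**Type I error.** Across the null simulations rank ANCOVA rejected in .0073 to .0096 of trials against a nominal .0083. With 20,000 trials the simulation standard error is √(.0083 × .9917/20,000) = .0006, so any excess is small.

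**The case against.** The strongest reply is that nothing is broken. The plan names one valid test per time point and a threshold, and the benefit of changing it rests on a correlation that the documents do not supply. Screening pain is osteoarthritis pain up to 21 days before surgery. Most outcomes are acute pain within two days, under a local anaesthetic technique and routine analgesia. If r is .2 or less, the gain is about 2 points of power. This stands, and it is why the point is a suggestion and not a defect.

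It can also be said that the gain is not free. Under the no-imputation rule, complete-case adjustment can do worse than the planned test, as the missing-score table shows. That holds for a carelessly specified adjustment; a covariate rule that keeps every patient with an outcome removes it.

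Three practical gaps also stand:
- The documents do not say which score in the 21-day window counts, or whether the clinic score uses the same 0-10 scale.
- A rank ANCOVA coefficient is not on the 0-10 scale, so an unadjusted interval beside an adjusted p-value could disagree with it. In simulation at r = .3 and 0.6 SD the two tests disagreed on significance in about 10% of trials.
- Adjustment does nothing for day-two scores never collected after discharge.

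Two figures above are slightly favourable. Simulated Mann-Whitney power at 0.712 SD on rounded scores is about 77%, not 80%. In ranks, the variance reductions are about 3.7%, 8.3% and 23.3%, not 4%, 9% and 25%. Neither changes the conclusion.

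**Conclusion.** The concern holds, as a missed efficiency and not an error. A scheduled pre-treatment pain score has no role in the primary analysis. At a 0.6 SD shift with 50 per arm, adjustment is worth about 2 points of power at r = .2, 5 at r = .3 and 14 at r = .5, and costs essentially nothing at r = 0. This rests on the assumed correlations and score distribution, and on a missing-baseline rule that keeps every patient with an outcome. It is worth considering, with medium confidence, because the true correlation is unknown and may vary by time point.

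**What to change.** Before outcomes are examined, amend section 4.7 as follows:

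1. **Test.** At each of the six postoperative times, regress the rank of resting pain on treatment and the rank of screening resting pain. Test the treatment term at .0083, two-sided. Use screening ambulating pain in the same way at the five ambulating times. Leave the multiplicity rule unchanged.
2. **Missing screening score.** Assign the mean rank of the covariate, both arms pooled, and keep the patient. Describe this as an exception to the no-imputation rule for the covariate only; outcomes stay unimputed.
3. **Covariate definition.** State which score in the 21-day window is used, for example the last recorded before surgery, and confirm that it is on the 0-10 scale.
4. **Reporting.** Keep the planned confidence intervals and add a baseline-adjusted difference on the 0-10 scale with its interval. Report the unadjusted Mann-Whitney test as a sensitivity analysis, and say that the adjusted test decides.

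The cost is SAP wording and a little more analysis. No patients, visits or measurements are added beyond those in Table I.

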1.0 BACKGROUND AND SIGNIFICANCE

Total hip arthroplasty can be associated with significant pain in the immediate postoperative period. In order to mitigate pain and subsequently facilitate patient mobilization and recovery, surgeons can use various methods of analgesia. Two current techniques are a more novel, psoas compartment block, which is gaining popularity for use in total hip arthroplasty with an anterior approach, and a periarticular local anesthetic injection. For a psoas compartment block, anesthetic is introduced directly into the iliopsoas and spreads to the lumbar plexus. For a periarticular local anesthetic infiltration, an anesthetic “cocktail” is injected at multiple spots to the surrounding tissue at the surgical site. To date, it is unclear which of these methods provides the best pain relief during the immediate postoperative recovery period.

It is theorized that the surgeon-delivered psoas compartment block can provide better and more complete pain relief than the “cocktail” injection since it is a consistent technique, and the injection specifically targets nerves that provide the operative area with sensation. Comparatively, the “cocktail” injection can be performed relatively consistently from one case to the next, but there is less knowledge of where the injectate will go and how effectively it will anesthetize the nerves – especially in the subcutaneous tissues.

The proposed study is a prospective, randomized clinical trial comparing patient-reported pain following total hip arthroplasty with a psoas compartment block versus a periarticular local anesthetic infiltration.

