3.0 HYPOTHESIS

- Our hypothesis is that the psoas compartment block will provide better pain relief (as measured by resting pain score) than the periarticular local anesthetic infiltration postoperatively at one or more of six specified post-operative times
- Additionally, we hypothesize less need for in-hospital opioids with a psoas compartment block within 24 and 24 to 48 hours postoperatively

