6.2 Risk Monitoring and Adverse Event Reporting

An adverse event (AE) is any noxious, unintended, or untoward medical occurrence that may appear or worsen in a subject during the course of a study. A serious adverse event (SAE) is any AE which:

- Results in death
- Is life-threatening (i.e., in the opinion of the investigator the subject is at immediate risk of death from the AE)
- Requires inpatient hospitalization or prolongation of existing hospitalization
- Results in persistent or significant disability/incapacity (a substantial disruption of the subject's ability to conduct normal life functions)
- A medical event that may jeopardize the subject or require medical or surgical intervention

The severity of adverse events (AEs) will be graded on a scale of 1 to 5 according to the National Cancer Institute (NCI) Common Terminology Criteria for Adverse Events ([The NCI Common Terminology Criteria for Adverse Events, Version 4.0 [NCI CTCAE]). The PI will determine the relationship between the administration of the block and the occurrence of an AE/SAE as unrelated, probably not related, probably related, or definitely related.

The participant will be monitored for risks and AEs in the hospital as standard of care. The PI and surgeon co-investigators will be responsible for tracking the occurrence of AEs while the patient is in-hospital. After discharge through the first follow-up appointment the patient will be monitored for hospital readmissions and asked to notify the PI of the occurrence of any AEs. A final assessment of complications and AEs will be made at a 3 week follow-up visit in the clinic (Michigan Orthopaedic Institute).

AEs of grade 4 or 5 will be reported to the HIC within 7 days. They will also be reported to the chair of the internal safety monitoring committee within 7 days and he will make a recommendation as to whether the study should continue.

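### The single-step Bonferroni rule is valid, but Holm's step-down would identify more of the time points and opioid windows that differ, within the same 5% family-wise bound

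*Combined protocol and SAP*

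**What the plan says.** The hypothesis in Section 3.0 is that the block gives better resting pain scores "at one or more of six specified post-operative times". Section 4.6 collects scores "at 3 hours postoperatively, in the morning and afternoon on postoperative day one and two and at the post-operative clinic visit". Appendix I, Table I, puts the clinic visit at 3 weeks, as does Section 6.2.

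Section 4.7 states: "VAS Pain scores (resting, ambulating) will be compared between groups at each time point using a Mann-Whitney Rank Sum test". The correction is there to "account for repeated measures and control for a Type I error", and the rule is: "A p -value below $.05/6 = .0083$ at each individual postoperative time point will be considered statistically significant". Opioid use in total, to 24 hours and from 24 to 48 hours is judged against .05/3, printed as .017. No step-down rule is given. Section 4.7.1 bases 50 per group on literature and feasibility, and no effect size, SD, correlation or power is stated.

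**The concern.** Under single-step Bonferroni, every time point must pass .0083 however many others have already been shown to differ. Once some hypotheses are rejected, fewer remain that could be falsely rejected, so a divisor of six is stricter than 5% family-wise control requires. Holm uses this slack and keeps the same tests, data and hypotheses.

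The plan declares significance at each time point, so the report will say when the block helps and for how long. With a fixed sample and no power calculation, a more efficient rule for those statements is worth having. The same holds for the three opioid comparisons.

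**Working it through.** **Inputs from the documents.** Six postoperative resting scores (Section 4.6; Appendix I, Table I), three opioid comparisons and the two thresholds (Section 4.7), and 50 per group (Sections 4.0 and 4.4).

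**Assumptions.** Effects in SD units, as listed below; exchangeable correlation 0.5 (0 to 0.9 for the error rate); two-sided tests. Section 4.7 states sidedness only for the unadjusted tests: "For all other tests which do not include Bonferroni adjustment, a two-sided p -value < 0.05 will be considered statistically significant".

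**1. The plan's figures.** .05/6 = .00833, printed .0083, which reproduces. .05/3 = .01667, printed .017.

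**2. Holm's thresholds.** Order the p-values from smallest to largest and stop at the first failure.
- Six resting scores: .0083, .0100, .0125, .0167, .0250, .0500.
- Three opioid comparisons: .0167, .0250, .0500.

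**3. Why the 5% bound holds.** Suppose m0 of the hypotheses are truly null. When Holm first rejects one of them, only non-null hypotheses have been rejected before it, so the divisor is still at least m0 and that p-value is below .05/m0. The chance that any of m0 null p-values falls below .05/m0 is at most m0 × .05/m0 = .05, whatever their correlation. Every Holm threshold is at least .05/6, so Holm rejects everything that Bonferroni rejects.

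**4. Power at one time point under Bonferroni.** Mann-Whitney efficiency under normality is 3/π = .955, so the mean of Z is d × √(50 × .955 / 2) = 4.886d. The critical value at .0083 two-sided is 2.638.
- d = 0.5: 2.443 − 2.638 = −0.195, power 42%.
- d = 0.6: 2.932 − 2.638 = 0.293 (from unrounded values), power 61.5%.

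**5. Average power per truly different time, Bonferroni to Holm.** At least 200,000 simulated sets of six Z statistics per scenario, full data:
- five times at 0.6 SD, none at 3 weeks: 61.5% to 68.7%
- five times at 0.5 SD, none at 3 weeks: 42.2% to 48.3%
- five times at 0.4 SD, none at 3 weeks: 24.7% to 28.5%
- 3 hours and both day-one scores at 0.6 SD: 61.5% to 64.4%
- two times at 0.6 SD: 61.5% to 62.9%
- fading effect (.6, .5, .4, .2, .1, 0): 26.9% to 29.1%
- one time at 0.6 SD: 61.7% under both

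**6. Power for at least one of six.** It is identical under both rules in every simulated set, because Holm's first step is also .05/6. It is 77.3% with five times at 0.5 SD and 91% at 0.6 SD.

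**7. Discrete scores and missing data.** Mann-Whitney tests on 2,000 simulated trials with integer 0 to 10 scores, SD 2 and a 1.0-point difference at five times: 38.7% to 44.6%. Table I, note b, stops second-day collection after discharge. With half of those scores missing the figures are 30.1% to 33.9%.

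**8. Error rate.** With no true difference anywhere, both rules give 4.9%, 4.2%, 3.3% and 2.2% at correlation 0, 0.5, 0.7 and 0.9. If five times differ by 0.5 to 0.6 SD, the chance of falsely declaring the null 3-week score is about 0.85% under Bonferroni and 2.5% to 2.9% under Holm, both inside 5%.

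**9. Opioid family.** With 0.5 SD on all three comparisons, power per test rises from 52% to 59%.

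**10. Scope of the 5%.** Section 4.7 applies .0083 to ambulating pain as well, which Table I schedules at five postoperative times. Over 6 + 5 = 11 tests the bound is 11 × .05/6 = 9.2%. The 5% therefore refers to resting pain only.

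**The case against.** The strongest reply is that nothing is broken. Bonferroni is prespecified and valid, and the hypothesis is met by any one of six times, for which Holm adds nothing. That stands: a reader might infer that Holm raises the chance of a positive trial, and step 6 shows that it does not. It is also fair that the larger gains need a sustained effect at several times and full data. The gain is small if the effect fades or is confined to one or two times, and missing second-day scores reduce it.

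Three stronger readings are also unsupported.
- **That Holm recovers what is lost because the scores are correlated.** Holm ignores correlation. Its error rate with no true difference falls with correlation exactly as Bonferroni's does (step 8).
- **That the 3-week score does not belong in the primary family.** Section 1.0 does ask which technique "provides the best pain relief during the immediate postoperative recovery period", but the objective in Section 2.0 sets no time limit and Section 3.0 counts six times. Removing one changes the hypothesis. It would raise single-time power at 0.5 SD only from 42.3% to 44.7% (.05/5 = .010).
- **That .017 is an error.** The exact fraction is printed beside it. Taken literally, 3 × .017 = .051, so this is display rounding.

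One cost is real but minor: Holm has no simple matching simultaneous confidence intervals. Section 4.7 does not say that its intervals are simultaneous, so they can stay as planned.

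**Conclusion.** This is an efficiency improvement to a valid method and does not correct an error. Holm keeps the 5% family-wise bound under any dependence and never rejects less. Its benefit is confined to deciding which time points and opioid windows differ once at least one has been shown to. For resting pain, average power per truly different time rises by about 6 to 7 points if five times differ by 0.5 to 0.6 SD, by about 2 points for a fading effect and by about 0 if one time differs. These sizes rest on assumed effects, correlation 0.5 and complete data on 50 per arm. The 5% bound, the dominance over Bonferroni and the unchanged power for one or more of six do not rest on those assumptions.

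**What to change.** In Section 4.7, before outcomes have been compared by group:
- **Resting pain (primary).** Order the six p-values, compare them in turn with .05/6, .05/5, .05/4, .05/3, .05/2 and .05/1, and stop at the first that fails. State that the 5% family-wise claim refers to this family.
- **Opioid use.** Do the same for the three comparisons with .05/3, .05/2 and .05/1, written as fractions.
- **Ambulating pain.** Name it a separate secondary family with its own Holm sequence, .05/5 to .05/1 for the five scheduled postoperative scores.
- State that all these tests are two-sided, if that is intended.

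The cost is a few lines of text. The tests stay as they are, and the thresholds can be applied by hand to the SPSS p-values. The confidence intervals stay as planned and should not be described as simultaneous. Whether the 3-week score stays in the primary family is the investigators' choice and is not part of this change.

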4.7.1 Sample Size

The sample size determination of 50 per group was based on a review of the literature and feasibility. [name] has provided justification for a lack of sample size analysis (see Appendix I).

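### Time to readiness for discharge has no rule for a patient who leaves before meeting all eight criteria; dropping that patient can shrink, inflate or create a difference between arms

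*Combined protocol and SAP*

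**What the plan says.** All references are to the combined protocol and SAP.

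- **Definition (4.6 Data Collection).** The outcome is listed as "Readiness for discharge (days), requiring the following", followed by eight criteria. They cover pain score and route of narcotic, eating, nausea, catheter, wound, acute medical problems, mobility ("The ability to independently transfer and walk 100 feet") and vital signs. Length of hospital stay is a separate variable in the same list.
- **Schedule (4.6).** "Readiness for discharge will be assessed in both the morning and evening of each postoperative day". No last assessment is stated. Readiness has no row in the schedule of events (Appendix I, Table I).
- **Test (4.7 Statistical Analyses).** The plan says that the recovery and symptom scores, "as well as the time to readiness for discharge, will be compared between groups with the" t-test or the Mann-Whitney test, whichever is appropriate. No Bonferroni adjustment applies to this endpoint, so "a two-sided p -value < 0.05 will be considered statistically significant".
- **Missing data (4.7).** "Missing data will be treated as such; there will be no imputation".
- **Size (4.7.1 Sample Size).** "The sample size determination of 50 per group was based on a review of the literature and feasibility". No power, effect size, standard deviation or event rate is given for readiness.

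No section says what value is given to a patient who leaves before all eight criteria are met. There is no censoring rule, worst rank or assessment of readiness after discharge. The documents also do not say whether discharge depends on the eight criteria, or how often patients leave without meeting them.

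**The concern.** Time to readiness is a time-to-event outcome, and discharge ends its observation. A patient who leaves unready is not simply missing: the trial knows that the readiness time, if any, lies after discharge. A t-test or Mann-Whitney test cannot use that partial information, and with no imputation the patient is removed.

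Removal matters because it can depend on both the outcome and the arm. Pain is one of the eight criteria, and pain is what the two techniques are meant to change. If patients in both arms leave at about the same time, the arm with slower recovery loses more of its late values and the difference shrinks. If one arm tends to leave earlier, that arm loses more of its slow patients and looks faster than it is. The plan guards against neither case. The one related extra analysis in 4.7, an exploratory subgroup that leaves out stays of more than 3 days, does not address patients with no readiness time.

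**Working it through.** **No figure to reproduce.** The documents give no number for this endpoint. The two Bonferroni thresholds in 4.7 (.05/6 = .0083 and .05/3 = .017) are correct but belong to pain and opioid use.

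**Inputs from the documents.** 50 per arm; 1:1 allocation; Mann-Whitney as one of the two planned tests; two-sided 0.05; no imputation; assessment twice a day.

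**Assumed inputs, not in the documents.** Readiness times are log-normal with log-SD 0.45, rounded up to half-days. Medians are 1.6 v 2.0 days when there is a true effect and 1.8 v 1.8 when there is none. Departure patterns are as in the table.

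**Share with no value.** If everyone not ready by day c has left, the share missing in an arm with median m is 1 − Φ(ln(c/m)/0.45).

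- c = 3, m = 1.6: ln(1.875)/0.45 = 1.40, so 8%.
- c = 3, m = 2.0: ln(1.5)/0.45 = 0.90, so 18%.
- c = 4, m = 1.6 and 2.0: 2.04 and 1.54, so 2% and 6%.
- m = 1.8 with c = 2.5 in one arm and c = 4 in the other: 0.73 and 1.77, so 23% and 4%.

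**Simulated rejection rates.** Each main scenario used 4000 trials; the Monte Carlo standard error is at most √(0.5 × 0.5/4000) = 0.8 points. Where two values appear, they come from two separate simulations. A dash means not computed.

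| Who has no value | Missing, arm A v B | Complete data | Dropped (plan) | Log-rank, censored at discharge | Mann-Whitney, ranked last | Mean difference in days, complete → dropped |
|---|---|---|---|---|---|---|
| True effect; not ready by day 4 | 2% v 6% | 64–66% | 55–56% | – | 66% | 0.44 → 0.33 |
| True effect; not ready by day 3 | 8% v 18% | 65–66% | 40–42% | 63% | 65% | 0.44 → 0.23 |
| True effect; not ready by day 2.5 | 16% v 31% | 65% | 31% | – | 64% | 0.44 → 0.17 |
| True effect; 30% have an early departure day unrelated to readiness | 14% v 19% | 66% | 57–58% | 58% | 52% | 0.44 → 0.43 |
| True effect; 10% missing at random | 10% v 10% | 66% | 61% | – | 47–48% | 0.44 → 0.44 |
| True effect; faster arm leaves by day 2.5, other by day 4 | 16% v 6% | 66% | 93% | – | 48% | 0.44 → 0.55 |
| No effect; arm A leaves by day 2.5, arm B by day 4 | 23% v 4% | 5–6% | 36–39% | 5% | 7% | 0.00 → 0.30 |

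**Reading the table.**

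1. With common departure days, dropping shrinks the difference and costs power. The loss is about 10 points at 2% v 6% missing and about 25 points at 8% v 18%.
2. When departure is unrelated to readiness, the difference is almost unchanged and the loss is mainly one of sample size.
3. When one arm leaves earlier, dropping exaggerates a real difference or produces a false one.
4. The log-rank test stayed close to complete-data power at 8% v 18% missing, held the 5% level when one arm left earlier, and matched dropping when departure was unrelated to readiness.
5. Ranking unready patients last works well when they really are slow, and loses power when they are not (47–48% against 61% for dropping).

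**The case against.** The strongest reply has four parts.

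- **Such patients may hardly exist.** The list is titled as readiness for discharge, and practice may follow it. This stands: the documents neither make discharge depend on the criteria nor say that patients leave without meeting them. With very few unready discharges the loss is small. In a second assumed model (gamma times, 8-hour shift), 2% v 4% missing gives 78% power when dropped against 81% when ranked last.
- **The dropped patients need not be the slowest.** A reader might infer that the rule discards the slowest patients and so can only hide a difference. The documents do not support this. Such a patient is known only to be unready at departure and may have left early; a footnote to Table I foresees discharge before the second-day time points. The table above also shows bias in the opposite direction.
- **The unit.** A reader might infer from the unit of days that twice-daily assessments are rounded to whole days and half the resolution is lost. No rounding rule is stated, and a half-day can be written in days, so this is not part of the point.
- **Importance.** Readiness is absent from the objectives and hypotheses (2.0, 3.0) and is neither the primary nor the secondary outcome. This stands and limits the priority.

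The gap itself survives: the stated test and the stated missing-data rule together remove a patient about whom the trial has information.

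**Conclusion.** The point holds as a minor one. The definition in 4.6 gives no readiness time to a patient discharged before meeting all eight criteria, and 4.7 then drops that patient. The result can be biased in either direction, depending on who leaves unready and whether departure differs by arm.

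The size is unknown, because the rate of unready discharge is not given. Under the assumed log-normal times it runs from negligible, if almost nobody leaves unready, to a fall in power from about 65% to 40% at 8% v 18% missing. With no true effect and one arm leaving earlier (23% v 4% missing), about 36% of trials falsely reject. These figures illustrate the mechanism and do not predict this trial. No primary or secondary conclusion depends on the endpoint.

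**What to change.** **In 4.6.** Record the date and session (AM or PM) at which all criteria are first met. Otherwise record *discharged, not ready* with the discharge time.

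**In 4.7.** Replace the t-test or Mann-Whitney comparison of this endpoint with wording such as:

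> Time to readiness for discharge will be analysed in all operated patients by randomised group. Patients discharged before meeting all criteria will be censored at discharge. Groups will be compared by Kaplan-Meier estimates and a two-sided log-rank test at 0.05. The number discharged not ready will be reported for each group. As a sensitivity analysis, a Mann-Whitney test will rank these patients later than all observed times.

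**Cost.** One field on the data form and a few sentences in 4.7, with no extra visits.

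**Downsides.** Medians replace means. Censoring assumes that departure is unrelated to later readiness. Ranking last assumes that unready patients are slow, and loses power if they are not. The two analyses rest on different assumptions, so both should be reported. If few patients leave unready, they should agree closely.
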